4.1 Eligibility/Inclusion Criteria

1. Participants must have histologically confirmed small cell lung carcinoma not amenable to initial concurrent radiotherapy (extensive-stage disease).
2. Participants may have evaluable or measurable disease, defined as at least one lesion that can be accurately measured in at least one dimension (longest diameter to be recorded for non-nodal lesions and short axis for nodal lesions) as ≥ 20 mm with conventional techniques or as ≥ 10 mm with spiral CT scan, MRI, or calipers by clinical exam. See Section 7.0 for the evaluation of measurable disease.
3. Participants in cohort B must have completed 1 cycle of systemic chemotherapy. Therapy with the combination must start no sooner than 3 weeks from the last dose of chemotherapy and no later than 5 weeks from the last dose of chemotherapy. Participants in cohort B must not have had progression of disease prior to the start of therapy.
4. Participants in cohort C must have completed systemic therapy (4-6 cycles cisplatin or carboplatin + etoposides) and NOT be a candidate for consolidation thoracic radiotherapy or PCI. Participants in cohort C must initiate therapy with pembrolizumab within 6 weeks of the last dose of chemotherapy (therapy must not start within 2 weeks from the last dose). Participants in cohort C must not have had progression of disease prior to the start of therapy.
5. Participants in cohort D must have completed systemic therapy AND have completed either consolidation thoracic radiotherapy or PCI or both completed either consolidation thoracic radiotherapy or PCI or both. Participants in cohort D must initiate therapy with pembrolizumab within 6 weeks of the last dose of radiation. Therapy must not start within 2 weeks from the

last dose. **Consolidation radiotherapy dose must NOT be more than 3000 cGy.**
 Participants in cohort D must not have had progression of disease prior to the start of therapy.

6. Age > 18 years.
7. ECOG performance status ≤ 2 (Karnofsky $\geq 60\%$, see Appendix A)
8. Life expectancy of greater than 3 months.
9. Participants must have normal organ and marrow function during screening and on Cycle 1, day 1 as defined below:

Table 1 Adequate Organ Function Laboratory Values

System	Laboratory Value
Hematological	
Absolute neutrophil count (ANC)	$\geq 1,500$ /mcL
Platelets	$\geq 100,000$ / mcL
Hemoglobin	≥ 9 g/dL or ≥ 5.6 mmol/L without transfusion or EPO dependency (within 7 days of assessment)
Renal	

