Serum creatinine OR Measured or calculated ^a creatinine clearance (GFR can also be used in place of creatinine or CrCl)	≤ 1.5 X upper limit of normal (ULN) OR ≥ 60 mL/min for subject with creatinine levels > 1.5 X institutional ULN
Hepatic	
Serum total bilirubin	≤ 1.5 X ULN OR Direct bilirubin \leq ULN for subjects with total bilirubin levels > 1.5 ULN
AST (SGOT) and ALT (SGPT)	≤ 2.5 X ULN OR ≤ 5 X ULN for subjects with liver metastases
Albumin	≥ 2.5 mg/dL
Coagulation	
International Normalized Ratio (INR) or Prothrombin Time (PT)	≤ 1.5 X ULN unless subject is receiving anticoagulant therapy as long as PT or PTT is within therapeutic range of intended use of anticoagulants
Activated Partial Thromboplastin Time (aPTT)	≤ 1.5 X ULN unless subject is receiving anticoagulant therapy as long as PT or PTT is within therapeutic range of intended use of anticoagulants
^a Creatinine clearance should be calculated per institutional standard.	

10. Availability of a diagnostic or pre-chemotherapy tissue biopsy is required (cytologic specimens or bone biopsies not accepted). This biopsy must be within 6 weeks of starting initial therapy. A minimum of 20 5 µm slides or block is required.
11. Participants in cohorts B-D must be willing to provide tissue from a newly obtained core or excisional biopsy of a tumor lesion. Newly-obtained is defined as a specimen within 4 weeks to initiation of treatment and AFTER the last dose of any prior therapy.
12. Participants with treated brain metastases are allowed. Radiation must be completed at least 2 weeks prior to pembrolizumab dosing and participants must not require ongoing steroids. Participants with untreated brain metastases that are all <5 mm with no clinical symptoms or vasogenic edema may be allowed on study on a case-by-case basis on discussion with sponsor. These participants will require MRI monitoring every 6 weeks to ensure stability.

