6.6.5 Tumor Imaging and Assessment of Disease

CT scan or MRI (as indicated) will be performed at baseline (within 28 days of initiation of treatment) and after every 2 cycles. Brain MRI should be performed during screening. All scans will be subjected to RECIST 1.1 evaluation and modified RECIST (ir RECIST 1.1)

Participants in cohorts A and B should have brain MRI performed during standard planned radiologic assessment at the completion of chemotherapy.

Participants in cohort C and participants in cohort A and B who do not have brain metastases after completion of chemotherapy and DO NOT undergo prophylactic cranial irradiation should have brain MRI performed every 12 weeks during planned radiologic assessments (after completion of chemotherapy).

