Vital signs	X	X	X	X	X	X		X ^g		X
Height	X	X	X	X	X	X				X
Weight	X	X		X	X	X				X
Performance status	X	X		X	X	X		X ^g		X
CBC w/diff, plts ^d	X	X	X	X	X	X		X ^g		X
Serum chemistry ^e	X	X	X	X	X	X		X ^g		X
EKG	X									
Adverse event evaluation	X	X	X	X	X	X	X	X ^g	X ⁱ	X
Tumor measurements/radiologic evaluation ^f	X			X	X	X		X ^g		X
Pulmonary Function Tests	X									
B-HCG	X ^e									X ^e
Tumor (archival) biopsy ⁱ	X									
Tumor biopsy (pre-treatment) ^j	X									
Tumor biopsy (post-treatment), optional						X ^h				
Blood samples for correlative studies		X ^k	X ^k		X ^k	X ^k				X ^k

^aPembrolizumab will be given on day 1 of each cycle. Carboplatin or cisplatin will be given on day 1 of each cycle. Etoposide will be given on days 1, 2, and 3 of each cycle.

^bCohort A participants will be treated with combination chemotherapy + pembrolizumab for a minimum of 4 and a maximum of 6 cycles. Cohort B participants will be treated for a minimum of 3 and a maximum of 5 cycles of combination therapy if they had only one cycle prior to study and a minimum of 2 or maximum of 4 if they had 2 cycles of therapy prior to study.

^cContinued maintenance pembrolizumab will be given on day 1 of each cycle after completion of chemotherapy with 1st dose 3 weeks after last cycle day 1 up through a maximum of 17 cycles following completion of chemotherapy. Interruption of therapy for planned radiation may occur as detailed in sections 5.5.5.1 and 5.11.1

^dSee Table 5 for details.

^eSee Table 5. BHCG, Free T4, T3, PT/PTT, uric acid will be drawn at screening only and thereafter as clinically indicated.

^fRadiologic assessment should include chest/abdomen/pelvis CT scan at baseline following by CT scan or MRI as appropriate to follow known areas of disease. Participants who have untreated brain metastases should have brain MRI at every scheduled radiologic assessment. For participants who DO NOT have baseline brain metastases, brain MRI should be performed on the planned radiologic assessment after completion of chemotherapy. For participants who do not have brain metastases after completion of chemotherapy and DO NOT undergo prophylactic cranial irradiation, brain MRI should be performed every 12 weeks following the completion of chemotherapy. Other radiologic assessments should occur every 6 weeks (within 7 days prior to every other cycle—prior to cycle 3, 5, 7, 9, etc).

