^bSee Table 5 for details.

^cSee Table 5. Free T4, T3, PT/PTT, uric acid will be drawn at screening only and thereafter as clinically indicated.¹

^dRadiologic assessment should include chest/abdomen/pelvis CT scan at baseline following by CT scan or MRI as appropriate to follow known areas of disease. For participants in cohort C (who do not have brain metastases after completion of chemotherapy and DO NOT undergo prophylactic cranial irradiation) brain MRI should be performed every 12 weeks following the completion of chemotherapy. Other radiologic assessments should occur every 6 weeks (within 7 days prior to every other cycle—prior to cycle 3, 5, 7, 9, etc).

^eIn the follow-up phase, exam, VS, laboratory assessments, and radiologic assessments should occur every 6 weeks for up to 18 weeks and then every 12 weeks thereafter.

^fParticipants who proceed to second course phase of treatment (re-treatment after progression with no intervening therapy) should sign consent for second-course phase and meet eligibility requirements prior to initiation of treatment. During treatment, assessments (laboratory, radiographic, blood collection) should follow schedule of maintenance pembrolizumab cycles. At the time of SECOND PROGRESSION, end-of-treatment, safety follow-up, and survival follow-up assessments should be as for 1st progression.

^gArchival biopsy with adequate tissue REQUIRED prior to starting on study (minimum 20 5 um slides)

^hParticipants who proceed to second course phase of treatment (re-treatment after progression with no intervening therapy) should sign consent for second-course phase and meet eligibility requirements prior to initiation of treatment. During treatment, assessments (laboratory, radiographic, blood collection) should follow schedule of maintenance pembrolizumab cycles. At the time of SECOND PROGRESSION, end-of-treatment, safety follow-up, and survival follow-up assessments should be as for 1st progression.

^jPre-treatment biopsies should be fresh biopsies for at minimum 4 participants in each cohort. For these participants, FNA in addition to core-needle biopsy (minimum 3-4 cores—see section 6.6.7.1 for specific requirements. For all participants, biopsies should be within 4 weeks of starting treatment with pembrolizumab and AFTER the last dose of prior therapy.

^kBlood samples will be drawn at the time of venipuncture during routine clinic visits. See section 6.7.4 for details.

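### The plan states no surveillance brain MRI for cohort D participants without PCI and without known brain metastases, so their CNS progression, and hence PFS shown by cohort, is ascertained less fully than in non-PCI participants of cohorts A to C

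*Combined protocol and SAP*

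**What the plan says.** **Brain imaging.** Section 6.6.5 applies to every cohort at entry: "Brain MRI should be performed during screening". The 12-weekly rule then goes to "Participants in cohort C and participants in cohort A and B who do not have brain metastases after completion of chemotherapy and DO NOT undergo" PCI. The A/B calendar (Section 7, footnote f) agrees: for those without brain metastases after chemotherapy who "DO NOT undergo prophylactic cranial irradiation, brain MRI should be performed every 12 weeks following the completion of chemotherapy". The C/D calendar, footnote d, names cohort C alone: "For participants in cohort C (who do not have brain metastases after completion of chemotherapy and DO NOT undergo prophylactic cranial irradiation) brain MRI". Otherwise footnote d asks for baseline chest, abdomen and pelvis CT, followed by CT or MRI of disease sites already known.

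**Who is in cohort D.** Section 4.1, item 5, admits participants who "completed either consolidation thoracic radiotherapy or PCI or both". Section 5.3 says the same. Section 2.1 describes thoracic radiation with PCI optional. PCI is therefore not an entry condition.

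**Brain metastases at entry.** Section 4.1, item 12, allows small untreated lesions case by case, in any cohort: "These participants will require MRI monitoring every 6 weeks to ensure stability". The A/B footnote carries a matching sentence: "Participants who have untreated brain metastases should have brain MRI at every scheduled radiologic assessment". The C/D footnote has none.

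**PFS.** Section 8.1.6 gives one definition for all cohorts, from registration to progression or death, with censoring at the last disease evaluation. Section 3.3 reports median PFS overall, stratified by cohort, against a historical 5.4 months. Section 2.2 adds PFS at 3 and 6 months. Sections 5.9 and 5.11.2 let treatment continue after isolated CNS progression but do not remove it as a PFS event.

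**The concern.** Within cohorts A and B, and in footnote d's own parenthesis about cohort C, the reason for surveillance MRI is that the participant had no PCI. A cohort D participant with thoracic radiotherapy only is in the same position, yet no rule is stated and no reason is given. The group is foreseeable. Section 1.1.1 says PCI is not a settled standard and refers to data in which MRI monitoring was used, and Section 5.11.2 anticipates isolated CNS progression in participants who had no PCI.

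The consequence is a difference in ascertainment. In non-PCI participants of A to C, asymptomatic CNS progression is found at a scheduled scan. In the D subgroup it is found when symptoms appear, or not at all if extracranial progression or death comes first. The censoring rule does not correct this, because a body scan counts as a disease evaluation although the brain was not imaged. The error runs one way: it lengthens observed PFS in part of cohort D when the four cohorts are set side by side.

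**Working it through.** **Step 1: the schedule, for participants without brain metastases.**

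| Group | Scheduled brain MRI after screening | Source |
|---|---|---|
| A/B, no PCI | end of chemotherapy, then every 12 weeks | 6.6.5; A/B footnote f |
| A/B, PCI given | end of chemotherapy only | 6.6.5; A/B footnote f |
| C (no PCI by definition) | every 12 weeks | 6.6.5; C/D footnote d |
| D, PCI given | none stated | – |
| D, thoracic radiotherapy, no PCI | none stated | – |

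Participants with untreated brain metastases have 6-weekly MRI in every cohort (4.1 item 12). The gap is therefore the last row only, compared with the non-PCI rows for A to C. The plan has no figure on this point to reproduce.

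**Step 2: an illustration of size.** From the documents: median 5.4 months (3.3), body scans every 6 weeks, brain MRI every 12 weeks. Assumed, because the documents give neither: the share of progressions that are CNS first (10, 20, 30%) and the mean delay from CNS progression to symptoms (2, 4, 6 months, exponential).

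- Hazard: ln 2 / 5.4 = 0.128 per month; true progression time T is exponential.
- Scan intervals: 42/30.44 = 1.38 months (body) and 84/30.44 = 2.76 months (brain).
- Extracranial progression is dated at T rounded up to the next body scan.
- CNS progression with MRI is dated at the earlier of the next MRI and T + delay. Without MRI it is dated at T + delay.

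Observed 6-month PFS, with MRI → without (400,000 draws per CNS share):

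| CNS-first share | delay 2 months | 4 months | 6 months |
|---|---|---|---|
| 10% | 49.2 → 50.4% | 49.2 → 51.4% | 49.2 → 52.1% |
| 20% | 49.1 → 51.4% | 49.1 → 53.7% | 49.2 → 55.0% |
| 30% | 49.2 → 52.7% | 49.2 → 56.0% | 49.3 → 57.9% |

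The shift runs from 50.4 − 49.2 = 1.2 points to 57.9 − 49.3 = 8.6 points. This model does not let later extracranial progression reveal a CNS-first participant, so it leans high. A version with competing CNS and extracranial progression (CNS share 15–35%, delay 2–4 months) gives 50.6–55.6% against about 49.1–49.2%, a gain of about 1.5 to 6.5 points.

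The simulated median moves from 5.52 to between 6.54 and 7.42 months, but that overstates the effect. The fourth body scan falls at 4 × 1.38 = 5.52 months, where observed PFS is already about 49%. A gain of about one point lifts the curve over 50% there and pushes the median towards the next scan at 6.90 months. The 6-month figure is the fairer summary.

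**Step 3: in context.**

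- If all 15 D participants were affected: 15 × 0.012 = 0.2 to 15 × 0.086 = 1.3 participants at 6 months.
- 95% half-width for 49% at n = 15: 1.96 × √(0.49 × 0.51 / 15) = 0.25, or ±25 points.
- Cohort D is 15/60 = 25% of the overall population, so the overall 6-month figure moves by at most about 0.25 × 1.2 = 0.3 to 0.25 × 8.6 = 2.2 points.

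**The case against.** The case against making much of this is substantial, and most of it stands.

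- **Brain imaging is not absent.** A reader might infer that D participants without PCI are never imaged again. The documents do not support that. Item 12 of Section 4.1 covers untreated brain metastases, footnote d allows MRI of known disease sites, Section 6.6.5 allows MRI as indicated, and Section 6 permits unscheduled procedures when clinically necessary. What is missing is scheduled surveillance in those without known brain disease.
- **Untreated lesions are not left unmonitored.** A reader might infer from the C/D footnote that small untreated metastases in C and D escape follow-up. Item 12 binds every cohort; the footnote merely fails to repeat it.
- **Cohorts A to C are not one uniform comparator.** Absence of PCI is already the stated criterion in A and B, and A/B participants given PCI also have no 12-weekly MRI. Cohort A participants without baseline brain metastases have no scheduled brain MRI until chemotherapy ends, at 4–6 three-week cycles (12–18 weeks). The simulation, with MRI every 12 weeks from entry, fits cohort C best.
- **PFS by cohort is not the main comparison.** The primary objective is PD-L1 expression. Section 9.1 specifies no between-cohort PFS test; its example of a logrank comparison is by baseline PD-L1. Cohort A registers before any treatment and D after chemotherapy and radiation without progression, so PFS from registration is not comparable across cohorts whatever the brain imaging.
- **The inputs are weak.** CNS share and symptom delay are assumed, and 5.4 months is a first-line historical figure applied to people who register later.

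None of this closes the gap. The imaging text and the cohort D definition do not fit together, and the direction of the resulting error is known.

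**Conclusion.** The omission is certain from the text: for cohort D participants without PCI and without known brain metastases, no brain MRI is scheduled after screening, whereas non-PCI participants of A to C have a 12-weekly rule. This can bias the secondary PFS summary upward in that subgroup. The subgroup's size is unknown (0 to 15), and the shift is illustratively about 1 to 9 points at 6 months under the assumptions above, shrinking in proportion if only part of cohort D is affected. It is small beside the ±25-point precision of a 15-person cohort.

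It would be tempting to say that the flaw undermines the trial's comparison of treatment timing. The documents do not support that: the primary endpoint is untouched, no between-cohort PFS test is prespecified, and cohort PFS already differs in its starting point. The point justifies a cheap addition to the reporting and a clarification, not a change of design.

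**What to change.** **Analysis.** Wherever PFS is shown by cohort, report extracranial PFS beside it: registration to first extracranial progression or death, with participants without an event censored at their last body scan. Participants who continue treatment after isolated CNS progression (5.11.2) stay under observation while body scans continue. Add a note that brain imaging differs by cohort and PCI status, and give the number of D participants without PCI. Body scans are planned every 6 weeks during treatment in all cohorts, so no new imaging is needed.

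The cost is one extra table. Some imbalance remains. In A/B, the radiation pause in Section 5.5.5.1 can separate doses by about 2 + 3 + 2 = 7 to 4 + 3 + 6 = 13 weeks (taking the full three weeks of radiation), and the assessment schedule restarts with the new cycle (5.3.2). Participants who leave treatment at CNS progression move to telephone survival follow-up, so their later body scans are lost.

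**Text.** The sponsor should reconcile Section 6.6.5 and C/D footnote d with the cohort D definition in Sections 2.1, 4.1 (item 5) and 5.3, and with 4.1 item 12, so that the brain-imaging rule for D participants without PCI is stated explicitly. What that schedule should be is for the investigators to set.

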8.1 Antitumor Effect—Solid Tumors

For the purposes of this study, participants should be re-evaluated for response every 6 weeks during therapy (and for 1st 18 weeks after therapy completion) followed by re-evaluation every 12 weeks. In addition to a baseline scan, confirmatory scans should also be obtained no less than 4 weeks following initial documentation of objective response (preferably at 6 weeks or next planned assessment).

Response and progression will be evaluated in this study using the new international criteria proposed by the Response Evaluation Criteria in Solid Tumors (RECIST) guideline (version 1.1) [*Eur J Ca* 45:228-247, 2009]. Changes in the largest diameter (unidimensional measurement) of the tumor lesions and the shortest diameter in the case of malignant lymph nodes are used in the RECIST criteria.

8.1.1 Definitions

Evaluable for Target Disease response. Only those participants who have measurable disease present at baseline, have received at least one cycle of therapy, and have had their disease re-evaluated will be considered evaluable for target disease response. These participants will have their response classified according to the definitions stated below. (Note: Participants who exhibit objective disease progression prior to the end of cycle 1 will also be considered evaluable.)

Evaluable Non-Target Disease Response. Participants who have lesions present at baseline that are evaluable but do not meet the definitions of measurable disease, have received at least one cycle of therapy, and have had their disease re-evaluated will be considered evaluable for non-target disease. The response assessment is based on the presence, absence, or unequivocal progression of the lesions.

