2.2 Secondary Objectives

- To evaluate median and progression-free survival at 3 and 6 months with the addition of pembrolizumab to standard therapy
- To evaluate median overall survival and overall survival at 6 months with the addition of pembrolizumab to standard therapy
- To evaluate response rates at 6 and 12 weeks by RECIST 1.1 and irRECIST with the addition of pembrolizumab to standard therapy
- To evaluate safety profile of pembrolizumab in combination with standard therapy for small cell lung cancer.

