3.3 Secondary Study Endpoints

- To evaluate progression-free survival with the addition of pembrolizumab to standard therapy
 - endpoint: to evaluate median progression-free survival in overall population with stratification by cohort as compared to historical control of 5.4 months³¹
- To evaluate overall survival with the addition of pembrolizumab to standard therapy
 - Endpoint: to evaluate median overall survival in overall population with stratification by cohort as compared to historical control of 9.5 months.³¹
- To evaluate response rates by RECIST 1.1 and irRC (as adapted to RECIST 1.1³²) with the addition of pembrolizumab to standard therapy (for cohort A only)
 - Endpoint: response rate at 6 and 12 weeks after initiation of pembrolizumab therapy as measured by RECIST 1.1 and irRC (as adapted to RECIST 1.1³²)

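### The only response population defined (8.1.1) leaves out participants with no post-baseline assessment, and Section 9 names no other denominator; by default the response rate is biased upward, and 2.2 and 3.3 disagree on which cohorts it covers

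*Combined protocol and SAP*

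**What the plan says.** Section 8.1.1 sets the conditions for having a response classified. Only participants with measurable baseline disease who received at least one cycle and "have had their disease re-evaluated will be considered evaluable for target disease response". One exception follows: "Participants who exhibit objective disease progression prior to the end of cycle 1 will also be considered evaluable". Death without documented progression is not mentioned. The parallel definition for non-measurable disease carries the same condition ("have received at least one cycle of therapy, and have had their disease re-evaluated will be considered evaluable for non-target disease") and states no exception.

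On timing, Section 8.1 says "participants should be re-evaluated for response every 6 weeks during therapy", and the Section 7 calendar places the first on-treatment scan shortly before cycle 3.

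Section 9.1 mentions response only when relating it to baseline PD-L1, by Fisher's exact test or the rank sum test. It names no denominator for a response rate, no all-treated set and no handling of missing response.

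On the population, Section 2.2 has the objective "To evaluate response rates at 6 and 12 weeks by RECIST 1.1 and irRECIST with the addition of pembrolizumab to standard therapy", with no cohort limit. Section 3.3 gives the matching endpoint "for cohort A only".

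**The concern.** A rate computed only among participants who reach a repeat assessment conditions on something that happens after treatment starts and is related to outcome. Someone who dies or is lost before the first scan cannot appear as a responder, and under 8.1.1 does not appear as a non-responder either. The rate then describes those who got as far as a scan, not those who were treated.

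If the same set were used for the PD-L1 comparison in Section 9.1, early failures would also be missing from that analysis, in an already small sample.

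The cohort conflict matters because participants in B to D enter after chemotherapy, and in D also after radiotherapy. Their baseline scans therefore follow treatment. Shrinkage from that baseline is a different quantity from shrinkage measured from an untreated baseline in cohort A.

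**Working it through.** The plan states no target, expected value or precision for response, so there is no figure of its own to reproduce.

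**Who is left out.** Reading 8.1.1 with the follow-up sections:

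- *Objective progression before the end of cycle 1:* kept, by the stated exception.
- *Progression imaged later, but before the scheduled week 6 scan:* kept, because the scan is a re-evaluation.
- *Stopped for toxicity:* usually kept. Section 4.6.2 asks for final-visit activities at discontinuation, the Section 7 calendars for all cohorts list tumor measurements at end of treatment, and 6.6.9.4 continues imaging every 6 weeks.
- *Clinical decline without objective progression:* usually kept. Section 8.1.4.4 asks sites to keep trying to document progression after treatment stops.
- *Death or loss before any post-baseline scan, without documented progression:* left out.
- *New therapy before any post-baseline scan:* left out. Section 6.5.2 moves these participants to survival follow-up, which assesses survival status only.
- *First cycle not completed:* left out if receiving a cycle means completing it; the wording is ambiguous.

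**Size.** Let N be the treated participants with measurable disease, r the documented responders, and m those left out. The same r is in both numerators, so

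- all-treated rate = r/N
- evaluable-only rate = r/(N−m)
- ratio = N/(N−m), which cannot be below 1.

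Inputs: N = 15 per cohort (Section 4.4), assuming all have measurable disease, although criterion 2 in 4.1 also admits evaluable disease. I take m = 1 to 3, with 3 borrowed from the Section 9.1 assumption that 12 of 15 yield results. That assumption concerns inability to continue therapy or undergo biopsy, so it only bounds the illustration. Values of r are assumed.

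Ratios: 15/14 = 1.07, 15/13 = 1.15, 15/12 = 1.25.

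| r (assumed) | r/15 | m = 1 | m = 2 | m = 3 |
|---|---|---|---|---|
| 5 | 33.3% | 35.7% | 38.5% | 41.7% |
| 9 | 60.0% | 64.3% | 69.2% | 75.0% |
| 10 | 66.7% | 71.4% | 76.9% | 83.3% |

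At r = 9 the excess is 4.3, 9.2 or 15.0 percentage points. Exact 95% intervals are 32.3% to 83.7% for 9/15, 35.1% to 87.2% for 9/14, 38.6% to 90.9% for 9/13 and 42.8% to 94.5% for 9/12.

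**Is m of 1 or more plausible?** As a rough scale, assume exponential survival from the start of treatment at the 9.5-month historical median in 3.3. Six weeks is 6/4.345 = 1.381 months. The probability of death by then is 1 − 2^(−1.381/9.5) = 9.6%, or about 1.4 of 15, and the chance of at least one such death is 1 − 0.904^15 = 78%. This probably overstates m: entry requires a life expectancy above 3 months, and deaths with documented progression stay in the set.

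**Population.** With four cohorts of 15, the planned number for response is up to 60 under 2.2 and up to 15 under 3.3.

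**The case against.** The strongest reply is that 8.1.1 defines who is evaluable and never says the reported rate is responders divided by that set. That stands: the denominator is inferred. But no other response population is defined, and Section 9 does not supply one, so an analyst following the text would arrive at it.

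A reader might infer that anyone who dies, deteriorates or stops for toxicity before week 6 is lost from the rate. The documents do not support that. Imaging at end of treatment and in follow-up, together with the instruction in 8.1.4.4, means that those who stop for toxicity or decline are usually still assessed. Early documented progressors are kept explicitly.

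A reader might also infer that a pooled response rate across cohorts is planned. No section says so, and 3.3, the more specific text, already limits response to cohort A. The conflict with 2.2 is nevertheless real.

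Finally, response is secondary, with no target, comparator or decision rule, and the intervals above overlap almost entirely. This limits the consequence. It does not remove the bias, which runs in one direction whatever the sample size.

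**Conclusion.** The point holds in a limited form. The plan leaves the response denominator unspecified, and the only set it defines excludes participants with no post-baseline assessment and no documented progression, along with any who do not complete a cycle. Compared with counting them as non-responders, this inflates the rate by N/(N−m): 1.07, 1.15 or 1.25 for 1, 2 or 3 of 15.

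The direction follows from the arithmetic, on the view that participants who are never assessed are almost all non-responders. The size rests on assumed values of m and r. The conclusion also depends on the 8.1.1 set being used by default, which Section 9 neither states nor rules out. Nor does Section 9.1 say which set the PD-L1 comparison would use, so an effect there is possible but not established.

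Sections 2.2 and 3.3 contradict each other on cohorts and need reconciling. The primary PD-L1 analysis is untouched. The change is worth making because it is cheap, but it is not critical to the trial.

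**What to change.** - In Section 9, with a cross-reference in 8.1.1, define the response-rate denominator as all cohort A participants with measurable baseline disease who received at least one dose. Count those with no post-baseline assessment as non-responders.
- Keep the 8.1.1 evaluable set as a sensitivity analysis, and report how many participants it leaves out and why.
- Reconcile 2.2 with 3.3, so that both name the same population. Section 3.3 already gives cohort A only.

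The cost is a few sentences and no new data or visits. The reported rate may be slightly lower.
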